- Omega-3 triglycerides (standard formulation)
- Omega-3 triglycerides (interesterified formulation).

The n-3 fatty acid preparations to be used are all commercially available as supplements and will be provided in capsules. Approximately 1.5 g EPA plus DHA (approx. 1.1 g EPA and 0.4 g DHA) will be given per day. Subjects, researchers and clinical staff will be blinded to group allocation.

Inclusion criteria

- 1. Aged 18 to 45 years
- 2. Body mass index 20 to 32 kg/m^2
- 3. Not consuming fish oil or other oil supplements
- 4. Not eating more than one oily fish meal per week
- 5. Willing to adhere to the study protocol
- 6. Being able to provide written informed consent

Exclusion criteria

- 1. Aged < 18 or > 45 years
- 2. Body mass index $< 20 \text{ or} > 32 \text{ kg/m}^2$
- 3. Being diabetic (type 1 or type 2)
- 4. Use of prescribed medicine to control inflammation
- 5. Chronic gastrointestinal problems (e.g. IBD, IBS, celiac disease, cancer)
- 6. Allergic to fish
- 7. Participation in another clinical trial
- 8. Use of fish oil or other oil supplements

Subject participation schedule

Subjects who express an interest will be screened by telephone interview. If they fit the inclusion and exclusion criteria they will be sent the information sheet. They will be contacted about 7 days later to confirm their interest or not and if they remain interested an appointment will be made for them to visit the Wellcome Trust Clinical Research Facility, Southampton General Hospital. At the first (and all subsequent) visit, subjects will attend in the fasted state (no food or drink except water after 9 pm the previous evening).

Subjects will visit the Wellcome Trust Clinical Research Facility, Southampton General Hospital on six occasions each between 8 and 10 am. On each occasion they will be in the fasted state. Visits will be at study entry and after approx. one, two, four, eight and twelve weeks of supplementation. On each occasion blood (20 ml) will be taken into heparin; at the visit made at study entry height and weight will be measured. At the end of each visit subjects will be offered toast and a hot drink. Subjects will receive a supply of supplements along with instructions on how to take them at the first study visit.

Sample analysis

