- comparison of the change in DHA content of each of the plasma lipid pools and of mononuclear cells and red blood cells from study entry to week 12 between the different treatment groups (the primary outcome). This will be performed by one factor ANOVA.
- comparison of the change of the EPA and DHA contents of each plasma lipid pool and of mononuclear cells and red blood cells over time following consumption of n-3 fatty acids in each chemical form. This analysis will be performed using two-factor repeated measures ANOVA, the two factors being time and group (i.e. "treatment").
- comparison of the change over time in blood concentrations of inflammatory markers according to treatment group. This analysis will be performed using two-factor repeated measures ANOVA, the two factors being time and group (i.e. "treatment").

All statistical comparisons will be performed at the end of the study using SPSS.

12. Sample size calculation

The study is powered according to the anticipated change in EPA content of plasma phospholipids (this is similar to the anticipated change in EPA in mononuclear cells and in red cells). Based upon previous studies of this sort, a supplement providing 1.1 g EPA/day is expected to increase the EPA content of plasma phospholipids by 100% from approximately 1 to approximately 2% of total fatty acids. It is considered that a 25% lower incremental increase in EPA content is meaningful. Typical standard deviations for the incremental increase in EPA content of plasma phospholipids from our previous studies are approximately 0.25%. Thus, sample size was calculated using mean values of 1 and 0.75 for the two groups, respectively, and standard deviations of 0.25 for each group. A sample size calculator revealed that a sample size of 17 per treatment group will give 90% power of

detecting this effect (i.e. a 25% increase) as statistically significant, by a pairwise comparison and setting P < 0.05, as is usual. In order to allow for a drop-out rate of 20% 20 subjects per group will be recruited (100 subjects in total).

13. Safety assessments

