The supplements to be used are commercially available and are safe. The sole invasive procedure to be used is obtaining blood samples; this will be done by trained nursing staff limiting the likelihood of adverse events related to participation in the study. However if any volunteer reports any untoward medical occurrence this will be recorded on an adverse event or serious adverse event form and the PI informed immediately. If the investigator suspects that a serious adverse event is either a) related to the intervention or b) unexpected, the PI will report the event to the main REC and to a representative of the supplier of the supplements. An adverse or serious adverse event may result in the volunteer wishing to withdraw from the study or being unable to continue with the study schedule. In this case or any other instance in which a subject withdraws or is withdrawn from the study a volunteer withdrawal form will be recorded on the form. The subject will not be required to give any reason for withdrawing themselves from the study and will not be asked to do so by the investigator.

14. Stopping/Discontinuation of intervention

Completion of each subject's involvement in the study will be when the last blood sample is taken, which will be approx. 12 weeks after the subject entered the study. If there is any reason for discontinuing the intervention prior to its completion the PI will arrange for the research team to inform all volunteers immediately. The PI will also inform the sponsor and the main REC.

15. Monitoring

The project will be overseen and monitored by the Southampton University Hospitals Trust R&D Office.

Steps taken to ensure quality of research

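### Section 13 tells investigators not to ask why a subject withdraws, so a withdrawal caused by intolerance of one formulation can go unrecorded unless the subject volunteers it

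*Protocol*

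**What the plan says.** Three statements in section 13 (Safety assessments) matter here.

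- Adverse events are captured by spontaneous report: "if any volunteer reports any untoward medical occurrence this will be recorded on an adverse event or serious adverse event form".
- Adverse events are recognised as a cause of withdrawal: "An adverse or serious adverse event may result in the volunteer wishing to withdraw from the study".
- Subjects who withdraw themselves are not required to "give any reason for withdrawing themselves from the study and will not be asked to do so by the investigator".

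Between the second and third statements, section 13 calls for a withdrawal form in that case and for every other withdrawal. The sentence is garbled as it stands ("a volunteer withdrawal form will be recorded on the form"), and the content of the form is not described.

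Elsewhere, the participation schedule in section 9 describes the visit procedures: "On each occasion blood (20 ml) will be taken into heparin; at the visit made at study entry height and weight will be measured". It also mentions the supply of supplements and refreshments after each visit. Section 12 sets the drop-out allowance: "In order to allow for a drop-out rate of 20% 20 subjects per group will be recruited".

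**The concern.** Two separate rules share one sentence. That a volunteer need not explain a withdrawal protects the volunteer and is not at issue. That the investigator will not ask is a different rule, and it is not needed for that protection, because a subject who is asked can still decline.

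The rule makes no exception for withdrawals prompted by an adverse event, although the paragraph has just named these. As adverse event capture relies on the volunteer speaking first, the withdrawal conversation is the natural point at which an unreported problem would surface, and the text tells the investigator not to raise the question.

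The trial compares placebo with four omega-3 preparations. If one were less well tolerated, subjects stopping it would be an early sign. The protocol as written may register that they left without registering why. A statistical analysis plan cannot repair this later, since it cannot analyse reasons that were never sought.

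**Working it through.** No figure in the protocol is in dispute. The check is a reading of the passages together, plus one line of arithmetic for scale.

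**Step 1. Is the rule an instruction or an omission?** Section 13 says in terms that the investigator will not ask. A site that followed the text would not put the question, so this is a stated rule and not a detail left for later.

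**Step 2. Which withdrawals does it cover?** It covers subjects who withdraw themselves, including those who do so because of an adverse event. It does not cover subjects withdrawn by the study team, whose reason the team would know.

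**Step 3. Does another route in the protocol collect the information?**

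| Possible route | What the protocol provides | Closes the gap? |
|---|---|---|
| Adverse event form (section 13) | Completed if the volunteer reports an event | Only if the volunteer speaks first |
| Visits (section 9) | Blood at each visit, height and weight at entry; no adverse event enquiry listed | No |
| Discussion with research staff (section 16) | Participants may raise issues they have | Only if the volunteer speaks first |
| Withdrawal form (section 13) | Used for every withdrawal; content not stated | Unknown, and the reason may not be asked for |

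Each route that could capture the event depends on the subject offering it. The path to an unrecorded event is therefore open: the subject feels unwell on the capsules, says only that they wish to stop, is not asked why, and no adverse event form is raised.

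**Step 4. Scale.** Inputs are from section 12: drop-out allowance 20%, 20 subjects per group, 100 in total.

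- Per group: 0.20 × 20 = 4.
- Overall: 0.20 × 100 = 20.

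These are upper figures at the planned rate. They fall by the number of subjects who volunteer a reason and by the number withdrawn by the team. The protocol gives no basis for estimating either, nor for saying how many withdrawals would be due to intolerance.

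**Step 5. What can still be seen without reasons?** Subjects are randomised to known groups and each withdrawal generates a form, so withdrawals can be counted by group. What cannot be done is to say whether an excess in one group reflects tolerability or unrelated causes. With about 4 expected per group, counts alone are a weak guide, and the reasons would carry much of the information.

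**The case against.** The strongest case on the other side is that this is a 12-week study of commercially available supplements in healthy volunteers, that the rule favours the volunteer's autonomy, and that it contradicts no other sentence: an adverse event can cause a withdrawal and still be recorded when reported. The rule bars asking why someone is leaving. It does not bar asking about untoward events at any of the six visits. Tolerability is not among the objectives in section 8, and the content of the withdrawal form is not shown.

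Much of this stands. There is no strict contradiction in section 13, and the loss of information is possible, not certain. But nothing in the protocol says that staff will ask about events at visits, and section 13 itself undertakes to record adverse events whether or not tolerability is an objective. Autonomy is fully served by the right to decline.

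Three stronger readings are tempting, and the protocol does not support them.

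- **A reader might infer that the rule biases the week-12 comparison by a calculable amount.** If drop-outs in one form had an EPA rise lower than its completers by some amount d, the completer mean would be too high by 0.20 × d at 20% drop-out. The protocol gives no value for d. More importantly, the shift comes from the missing week-12 values and is the same whether or not reasons are recorded. It is not a measure of this point.
- **A reader might infer that nothing could be learned about whether drop-out relates to formulation.** Counts by group remain available, as Step 5 shows.
- **A reader might infer that every withdrawal would be unexplained.** Events that volunteers report go on an adverse event form and to the principal investigator at once, and withdrawals made by the team have known reasons.

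Nor does section 14 tie a decision to discontinue the intervention to individual withdrawal reasons, so an effect on that decision would be conjecture.

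**Conclusion.** The point holds as a limited weakness in data capture. Followed literally, section 13 allows a withdrawal caused by intolerance of one formulation to pass without an adverse event record and without a reason. At the plan's own drop-out allowance, up to about 4 of 20 subjects per group could leave with no reason on record, and the cause of any imbalance between groups could not then be judged.

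This rests on two assumptions: that sites apply the instruction as written, and that some subjects do not volunteer their reason. It makes no claim about the number of intolerance withdrawals or about the size of any bias in the primary comparison. The change is worth making because it is inexpensive and cannot be made good after the event; the trial does not fail without it.

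**What to change.** In section 13, delete the clause stating that the subject "will not be asked to do so by the investigator", with the conjunction before it. Replace it with wording to this effect: *Subjects need not explain a decision to leave. They will be invited to give a reason and asked whether any untoward medical occurrence contributed, and may decline to answer. Any such occurrence is entered on the adverse event form; the reason, or the word declined, is entered on the withdrawal form.*

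The garbled sentence about the withdrawal form should be rewritten at the same time. Because subjects and staff are blinded, the question can be put in the same neutral words in every group.

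The cost is one sentence in the protocol and one field on a form already in use. The downside is that some volunteers may find the question unwelcome; they remain free not to answer. The change touches no dose, schedule or rule for stopping the supplements. It would help to interpret drop-out, but it would not recover missing week-12 samples.
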